5.2 Part B

If, following Part A, the process is found to be an acceptable form of monitoring to patients, the study will continue to Part B. This will evaluate the potential for earlier diagnosis of AKI with intensive home monitoring of kidney function (plus standard of care monitoring) compared with standard of care only. The decision of whether to proceed to this stage of the study is described in further detail below. Participants who have been recruited to Part A of the study can continue to Part B if they so wish (and will be randomised).

Part B will enrol 60 patients being treated for cancer with potentially nephrotoxic anti-cancer therapies, randomised to either the intensive monitoring (device) group or the standard of care monitoring group, in a 1:1 ratio. Participants in both groups will be asked to complete a quality of life questionnaire at baseline. Both groups will receive standard of care monitoring of kidney function. In addition, participants in the intensive monitoring group will upload their creatinine reading three times per week (Mon/Wed/Fri) for 6 weeks. As in Part A, participants in the intensive monitoring group will be required to access the app on their own compatible device and upload their readings over their own internet connection. In both study arms, in line with scheduled clinic appointments (weeks B1, B3 and B6), blood and urine will be collected for exploratory biomarker analysis, along with renal function and cystatin C. When a participant attends a clinic appointment, a creatinine reading will be taken (either by the study participant or by a member of the study team) using the device, for comparison with the laboratory reading of creatinine taken that day.

During Part B of the study, when a participant has submitted their creatinine reading they will receive a successful submission message on the app and may receive feedback based on their reading (this depends on feedback from Part A of the study, performance of the amended algorithm from Part A and development of the smart phone application). As with Part A, participants will be directed to their

parent medical team if there is concern over their reading. Creatinine readings and AKI alerts from the algorithm will also be reviewed by the Chief Investigator once a week and highlighted to the parent medical team if there are concerns.

At the end of Part B, all participants in both groups will be asked to complete a quality of life questionnaire, and those in the intensive monitoring arm will also be asked to take part in a short interview and complete a questionnaire reviewing the process of home monitoring and sending in creatinine results, (as in Part A). As in Part A, all readings and other data stored on the device will be downloaded directly from the device at the end of Part B to confirm the accuracy and frequency of the readings uploaded via the app.

At the end of Part B, a short interview will be carried out with clinicians to explore their opinions towards home monitoring and the impact it could have on their treatment schedules for patients.

Each scheduled visit allows for a +- 1-week window to allow for possible variation amongst treatment regimens.

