4. STUDY AIMS AND OBJECTIVES

This study will be delivered in two sections: Part A and Part B. The aim of Part A is to assess whether intensive home monitoring of creatinine is an acceptable and feasible form of monitoring for patients. Part B of the study will aim to show earlier detection of deteriorating kidney function and AKI as compared to standard of care renal monitoring.

Table 2: Study objectives, outcomes and measures

Objectives	Outcome Measures	Timepoint(s) of evaluation of this outcome measure (if applicable)
Primary Objectives		
Part A: To evaluate patient acceptance of intensive home-monitoring of whole-blood creatinine.	Questionnaire and interview Absolute number of creatinine readings received-expected vs actual Time sample taken vs. time expected to take Value sent/received vs. value on device (when downloaded at the end of the study period)	Week 4
Part B: To evaluate the potential for earlier diagnosis of AKI/change in renal function with intensive home-monitoring of whole-blood creatinine.	Time from beginning of current cycle treatment to detection of AKI by amended algorithm or clinician/laboratory reading Severity of AKI at detection (as	Throughout study period
	per Kidney Disease Improving Global Outcomes AKI Work Group staging) Overall change in renal function from beginning to end of study period	

Secondary Objectives		
Part B: To assess whether intensive monitoring influences the change in kidney function over the study period compared to standard of care	Comparing kidney function at the beginning and end of the study	Weeks 1 and 6
Part B: To assess whether home monitoring of kidney function has a positive impact on a patient's quality of life.	Medical outcomes study short form 36 (SF-36) questionnaire	Week 6
Part B: To evaluate the adherence of patients to intensive home monitoring regimen	Absolute number of creatinine readings received Time sample taken vs. time expected to take Value sent/received vs. value on device (when downloaded at the end of the study period)	Week 6
Exploratory Objectives		
Part A: Using data gathered to improve and test amended AKI algorithm	Amended algorithm outcome vs clinician assessment Feedback and analysis from interviews and questionnaires	On completion of Part A
Part B: To explore the value of novel renal biomarkers in the cancer population for early detection and monitoring of AKI.	Urine and serum analysis	Throughout study period

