1.3 Format and scale of the data

Approximately 20 creatinine readings per study participant captured in encrypted electronic form. Baseline data capture in paper workbook and consolidated into excel workbook

Participant feedback from paper-based questionnaires.

Approximately 72 participants to be recruited (30 will be randomised in to the non-device group therefore will not be sending in creatinine readings)

2. Data collection / generation

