14.6 Participant Booklet

Getting help

If you have problems with the test kit, app, or answering the questions please get in touch so that we can help. To do this

- · Pop in to see us next time you're in hospital. We're in the new bit of the clinical trials unit. Go up ramp next to reception, turn right, we're next to the mosaic.
- Contact support: [contact]. This email is checked 9-5 throughout the working week.

The Christie Hotline

It is essential that you continue to contact your medical team as normal if you have any concerns about your health.

If you feel unwell, do not delay, call the Christie Hotline Immediately

[name]

Thank you

Kidney monitoring research How to take a reading at home

What we're doing

People with partly-working kidneys often don't get the choice of taking part in cancer trials because of worries over damaging their kidneys further. This means that there are fewer treatment options for people who have both cancer and kidney disease.

We want to understand whether people monitoring their kidneys at home via a simple blood test could help with this. Can it improve the understanding of what's happening with their kidneys and support they're given? If so, then this may eventually allow patients with partly-working kidneys to take part in cancer trials to improve treatment options of the future?

What you'll be asked to do

On Mondays, Wednesdays and Friday mornings for the next 8 weeks we would like you to check your kidneys by taking a 'creatinine reading' with the meter provided. Then send us the result using an app on your smart phone (designed for securely sending information). We'd also like to hear your feedback on the whole process at set points throughout the 8 weeks and through an informal interview at the end of the study.

This booklet aims to walk you through the use of the kidney monitoring kit and how to send your information in.

First: Testing the device itself

Take the test strips and bottles out of the fridge so that they are at room temperature before starting. Then wash your hands.

[figure not shown]
Step A: Put a new test strip in your meter. Press the left and right buttons until the screen says C1 as shown.

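### Part B ends at week 6 in Section 5.2 and Table 2 but at week 8 in Table 4, and the participant booklet asks for 8 weeks, so the end-of-study timepoint and the expected number of readings are each defined in two incompatible ways

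*Protocol*

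**What the plan says.** The protocol describes the Part B timetable in four places.

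- **Section 5.2** sets the monitoring period: "participants in the intensive monitoring group will upload their creatinine reading three times per week (Mon/Wed/Fri) for 6 weeks". Sampling in both arms is "in line with scheduled clinic appointments (weeks B1, B3 and B6), blood and urine will be collected".
- **Table 2 (Section 4)** agrees with Section 5.2. The secondary kidney-function comparison is at weeks 1 and 6, and quality of life, adherence, and the participant and clinician interviews are at week 6. Two entries do not name a final week. One is the primary-objective measure "Overall change in renal function from beginning to end of study period". The other is the time to AKI detection, which is evaluated over the whole study period.
- **Table 4 (Section 7)** has Part B columns for screening and weeks 1, 4 and 8. The last blood and urine samples, blood pressure, quality of life, usability questionnaire and interviews are all in the week 8 column. There is no column for week 3 or week 6.
- **The participant booklet (Section 14.6)** tells participants: "On Mondays, Wednesdays and Friday mornings for the next 8 weeks we would like you to check your kidneys". It does not say which part it belongs to.

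For Part A, Section 5.1 gives 4 weeks of readings, and Tables 2 and 3 both end at week 4.

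**The concern.** This is current protocol text, and the two timetables cannot both be followed. A site working from Table 4 would take the final creatinine sample and quality-of-life form at week 8. Table 2 evaluates those outcomes at week 6, and under Section 5.2 the home readings would already have stopped.

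Three things are at stake.

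1. **Renal-function change.** The primary-objective measure is tied only to the end of the study period, so its endpoint moves with the timetable. Section 9 rests the Part B sample size on creatinine levels and names no week either.
2. **AKI detection.** If the study period runs to week 8 while uploads stop at week 6, the last part of the comparison has standard monitoring in both arms.
3. **What participants do.** They act on the booklet, and it asks for more finger-prick readings than the protocol body specifies in either part.

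**Working it through.** **Inputs.** Three readings per week (Sections 5.1 and 5.2, booklet). Durations of 4 weeks (Part A, Section 5.1), 6 weeks (Part B, Section 5.2) and 8 weeks (booklet). Visit window of one week either side: "Each scheduled visit allows for a +- 1-week window to allow for possible variation amongst treatment regimens". Device users: 12 in Part A and 30 in the Part B device arm.

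**Sources side by side**

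| Source | Monitoring duration | Middle visit | Final visit |
|---|---|---|---|
| Section 5.2 | 6 weeks | week 3 | week 6 |
| Table 2, Part B | not stated | not stated | week 6 |
| Table 4 | not stated | week 4 | week 8 |
| Booklet, no part label | 8 weeks | not stated | not stated |
| Section 5.1, Tables 2 and 3, Part A | 4 weeks | – | week 4 |

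**Expected readings = 3 × weeks**

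- Part A body text: 3 × 4 = 12.
- Part B body text: 3 × 6 = 18 per participant, and 30 × 18 = 540 for the device arm.
- Booklet: 3 × 8 = 24 per participant, and 30 × 24 = 720 for the device arm.
- Excess if the booklet is followed: 24 − 18 = 6 readings per participant in Part B and 24 − 12 = 12 in Part A.

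**Visit windows = nominal week ± 1**

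- Middle visit: 3 ± 1 = weeks 2-4; 4 ± 1 = weeks 3-5. These overlap in part.
- Final visit: 6 ± 1 = weeks 5-7; 8 ± 1 = weeks 7-9. These meet only at week 7.

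**Gap between the last home reading and the final assessment, if Section 5.2 governs uploads and Table 4 governs visits**

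Assume that uploads fill weeks 1 to 6. The nominal gap is 8 − 6 = 2 weeks. With the window it runs from 7 − 6 = 1 week to 9 − 6 = 3 weeks. At the nominal gap, 2/8 = 25% of an 8-week study period would have no home monitoring in the device arm.

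**Does the data management plan settle it?** Section 14.5 gives the only stated count: "Approximately 20 creatinine readings per study participant captured in encrypted electronic form". Two ways of reading it:

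- *Per Part B device participant.* Six weeks gives 18 home readings, or up to 18 + 3 = 21 with one device reading at each of three clinic visits. Eight weeks gives 24, or up to 27.
- *Average over all 42 device users.* Six weeks in Part B gives (12 × 12 + 30 × 18)/42 = 16.3. Eight weeks gives (12 × 12 + 30 × 24)/42 = 20.6. Adding two clinic readings in Part A and three in Part B gives 19.0 and 23.3.

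An approximate 20 fits 6 weeks on the first reading. On the second it fits 8 weeks without clinic readings or 6 weeks with them. It does not decide between the schedules.

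**The case against.** The strongest reply is that the protocol has a governing version. Section 5.2 and Table 2 agree with each other on week 6, so a reader could treat Table 4 and the booklet as slips, with the visit window absorbing the difference. It can be added that Section 5.3 already foresees that the Part B duration may be amended, and that an analysis plan could fix the analysis timepoint.

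Part of this stands. The Part B endpoint is not undefined: week 6 is stated, and a reader who infers that no timepoint exists goes too far. The rest does not remove the conflict. The windows share a single week. A possible later amendment does not explain two schedules in the present text. An analysis plan cannot recover week 6 samples that were taken at week 8, or change what participants were told.

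Some stronger inferences are tempting but lack support:

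- **That Part A is also ambiguous.** The protocol body gives 4 weeks throughout; only the booklet differs.
- **That a fully adherent participant would score 12/24 = 50% in Part A or 18/24 = 75% in Part B and so endanger progression.** Those ratios take the numerator from one source and the denominator from another, and nothing in the protocol computes adherence that way. The 75% adherence factor in Section 5.3 concerns only the move from Part A to Part B. Expected-versus-actual wording also appears only for Part A; the Part B measure is "Absolute number of creatinine readings received", with no denominator.
- **That the figure of about 20 readings is itself an error.** It is compatible with 18 home readings plus up to three clinic readings.

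**Conclusion.** The concern holds as an internal contradiction. Part B has two incompatible timetables: 6 weeks with visits at weeks 1, 3 and 6, against visits at weeks 1, 4 and 8 with a booklet asking for 8 weeks. The final visit differs by two weeks and the expected count by six readings per participant (18 against 24). The end-of-study change in renal function and the AKI-detection period inherit that difference. In Part A the fault is confined to the booklet, which would ask for 24 readings where the protocol specifies 12.

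The gap of one to three weeks after home readings stop assumes that uploads follow Section 5.2 and visits follow Table 4. The booklet consequence for Part A assumes that the same unlabelled booklet is given out in both parts. The documents do not settle which duration is intended, and this point takes no position on it. It does not bear on whether the Part B sample size is adequate, which was not assessed here.

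It should be corrected before the trial proceeds, because sites and participants following different pages would collect different data.

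**What to change.** Before recruitment:

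1. Reconcile Section 5.2, Table 2, Table 4 and the booklet to one monitoring duration and one visit schedule per part.
2. Issue a corrected booklet for each part, labelled as such, with the duration that applies to that part.
3. State the resulting expected number of readings per participant for each part.
4. Name the week that closes the study period for the renal-function change and for AKI detection, in line with the reconciled schedule.

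The cost is a document correction and a revised booklet, handled through the amendment route in Section 10.7 where approval has already been given. The correction itself needs no change to the number of participants or the randomisation.

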5. STUDY DESIGN

5.7 Part A

Twelve patients being treated for cancer with potentially nephrotoxic anti-cancer therapies (according to the judgement of the CI) will be enrolled during Part A. Following consent, each will be trained on the use of the at-home creatinine detector and provided with the device to check their creatinine at home three times per week for 4 weeks. This will be in addition to the standard care they are receiving as part of their treatment. Participants will be advised to contact their parent medical team if they have any concerns regarding their health during the study period. The participants will upload their readings to the secure cloud environment 3 times a week (Monday/Wednesday/Friday) for 4 weeks. They will be required to use their own compatible smart phone or device to access the app, and to upload the data over their own internet connection.

Part A is an evaluation of a process that has not been tested in full before, along with a device that has not been used in this setting previously. The data gathered will be run through the amended AKI algorithm to look for evidence of AKI, participants will receive confirmation that the measurement has been successfully sent. Once a week, alerts from the algorithm and creatinine readings will be reviewed by the Chief Investigator and flagged to the parent medical team if there are concerns over a reading or alert.

At the end of week A1, participants will receive a phone call to ensure they are managing with the general process of sampling and sending results through the app, and to deal with any troubleshooting issues that may have arisen. At week A1 and A4 blood and urine will be collected for

exploratory biomarker analysis, along with renal function and cystatin C. When a participant attends a clinic appointment, a creatinine reading will be taken (either by the study participant or a member of the study team) using the device, for comparison with the laboratory creatinine reading taken that day.

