6. SELECTION OF STUDY POPULATION AND WITHDRAWAL CRITERIA

Participants for both Part A and Part B will be identified from the general oncology outpatient population, with an initial focus on the Head and Neck Outpatient clinics. Anecdotally, this group of patients are high risk for AKI due to the nature of the treatment (platinum-based therapies) and increased risk of severe dehydration due to treatments that affect swallowing. Patients who have taken part in Part A of the study can continue to Part B if they wish and will be randomised prior to their participation in Part B.

Inclusion criteria

- Provision of signed and dated, written informed consent prior to participation in the study.
- Aged at least 18 years
- Receiving treatment for cancer with potentially nephrotoxic anti-cancer therapies (according to the judgement of the CI)
- Individuals whose medical team consider to be medically stable and able enough to take part or designated carer who would be able to perform the tasks required.
- Willingness and ability to self-monitor creatinine using device at home or have a
 designated carer who would be able to perform the tasks required. Part A device will
 be the NovaBiomedical StatSensor®.
- Access to smart phone and willingness to use, without reimbursement of any potential additional costs incurred, their iOS/Android device for the collection and transmission of information.

Exclusion criteria

- Being an employee, or closely linked with an employee, of the device company
- Judgment by the Investigator that the individual should not participate if they are unlikely to comply with study procedures and requirements.

- WHO performance status > 2
- Pregnancy

If withdrawal from the study occurs, permission will be sought to use their existing study data as well as data which forms part of their routine clinical care for the remainder of the study period. This will not require any further participation from the subject for the purposes of the study.

Possible reasons for withdrawal:

- 1. Withdrawal of consent
- 2. Pregnancy
- Loss of capacity/ability to carry out study requirements as deemed by participants primary medical team

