7. STUDY PROCEDURES

Once a patient has agreed to take part in the study and informed consent is gathered the following will be gathered from medical records and the patient:

- 1. Baseline kidney function urea, creatinine and eGFR at point of diagnosis and 3 months previous
- 2. Significant past medical and surgical history
- 3. Previous cancer treatments relating to incident cancer diagnosis
- 4. Risk factors for AKI
- 5. Blood pressure at previous clinic attendances relating to incident cancer diagnosis
- 6. Urine collection and dipstick results at previous clinic attendances relating to incident cancer diagnosis
- 7. Concomitant medication and recent acute prescriptions

Table 3: Trial Procedures Part A

Procedures – Part A	Visits			
	Screening	Baseline Week 1 (+-1 week)	Week 2 (+- 1 week)	Week 4 (+- 1 week)
Informed consent	х			
Demographics (from medical notes)		х		
Medical history (from medical notes)		х		
Phone call		х		
Blood Pressure		х		Х
Urine Collection		х		Х
Blood Collection		х		Х
Usability Questionnaire				х
Workbook completion		х		х
Semi-structured interview				х

Table 4: Trial Procedures Part B

^{* -} intensive monitoring group only

Procedures - Part B	Visits			
	Screening	Baseline Week 1 (+-1 Week)	Week 4 (+- 1 week)	Week 8 (+- 1 week)
Informed consent	х			
Demographics (from medical notes)		x		

Medical history (from medical notes)	х		
Phone call*	x		
Blood Pressure	X	Х	х
Urine Collection	X	Х	х
Blood Collection	Х	Х	Х
Usability			x
Questionnaire*			
QoL Assessment	X		х
Workbook completion	X	Х	Х
Semi-structured interview – participant*			х
Clinician interview			x

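### The protocol does not ensure that the Part B baseline is taken before randomisation and before the first home reading

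*Protocol*

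**What the plan says.** - **Window.** Section 5.2 states for Part B: "Each scheduled visit allows for a +- 1-week window to allow for possible variation amongst treatment regimens". No visit is excepted. The visit tables in section 7 head the first column after Screening "Baseline Week 1 (+-1 week" (closing bracket cut here; Table 4 differs only in a capital letter), so the window covers baseline explicitly.
- **What is collected when.** In Table 4 the Screening column holds informed consent only. Study blood, urine, blood pressure and quality of life first appear in the Baseline Week 1 column. For renal sampling, section 5.2 says: "In both study arms, in line with scheduled clinic appointments (weeks B1, B3 and B6), blood and urine will be collected".
- **Outcomes that use this visit.** Table 2 defines the secondary kidney-function outcome as "Comparing kidney function at the beginning and end of the study" and times it at Weeks 1 and 6. Overall change in renal function over the study is also listed under the Part B primary objective. Quality of life is completed at baseline and at the end in both arms.
- **Intervention.** The intensive arm will "upload their creatinine reading three times per week (Mon/Wed/Fri) for 6 weeks".
- **Order of randomisation.** Section 5.4 describes the method but not its place in the visit sequence, and Table 4 has no randomisation row. Section 6 says that patients coming from Part A "can continue to Part B if they wish and will be randomised prior to their participation in Part B".
- **Arm-specific item.** The Baseline Week 1 column of Table 4 contains a phone call marked "intensive monitoring group only".

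**The concern.** A baseline is safe for measuring change only if neither the allocation nor the intervention can have touched it. Here a site can follow the protocol exactly and still collect the baseline after the participant has been told the arm and has begun home readings.

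The risk differs by outcome. Quality of life is self-reported, and one arm has a device and an app while the other does not, so participants know their arm. Reassurance from having the device, or disappointment at not having it, can shift the answers at once. If that shift is already in the baseline score, it is subtracted from the change. No earlier quality-of-life score exists to fall back on, so the loss cannot be repaired in the analysis.

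For kidney function the mechanism is slower. Any early benefit of monitoring that is already present at a late baseline is removed from the change-from-baseline contrast, which tends to pull it towards zero.

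**Working it through.** The plan gives no figure for this point, so the check is visit-window arithmetic and a reading of the visit order.

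**1. Home readings that can precede baseline**
- Inputs from section 5.2: 3 readings a week for 6 weeks, and a window of 1 week either side.
- Scheduled readings: 3 × 6 = 18.
- Assumption: home monitoring starts at the beginning of Week 1, whenever the visit takes place. The protocol does not state this.
- If the nominal visit is at the start of Week 1, the latest baseline follows 3 × 1 = 3 of 18 readings.
- If the nominal visit is at the end of Week 1, it follows 3 × 2 = 6 of 18.
- On the minus side of the window, the visit can fall before any reading.

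**2. Interval between first and last visit**
- With B1 and B6 (section 5.2): nominal 6 − 1 = 5 weeks; shortest 5 − 2 = 3; longest 5 + 2 = 7.
- With Weeks 1 and 8 (Table 4): nominal 8 − 1 = 7 weeks; range 5 to 9.
- The same window applies in both arms, and everyone is already on potentially nephrotoxic treatment at entry. This spread therefore adds noise to both arms; it does not favour one of them.

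**3. What dilution could look like for creatinine (illustration only)**
- Section 9 assumes means of 1.2 and 0.9 mg/dl with SD 0.2, a difference of 0.3. Section 5.2 gives 60 patients at 1:1, so 30 per arm.
- Assumptions: the effect builds linearly over the 6 weeks, and every intensive-arm baseline is late by t weeks. The change contrast is then 0.3 × (1 − t/6).
- t = 1: 0.3 × 5/6 = 0.25 mg/dl. t = 2: 0.3 × 4/6 = 0.20 mg/dl.
- SD of a change score: 0.2 × √(2(1 − ρ)), with the within-patient correlation ρ assumed. Power is for a two-sided 5% test (normal approximation).

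| ρ (assumed) | baseline on time | all 1 week late | all 2 weeks late |
|---|---|---|---|
| 0 | 98.4% | 92.8% | 78.2% |
| 0.5 | over 99.9% | 99.8% | 97.2% |

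These cases put every participant at the limit of the window, so they are not estimates. The protocol gives nothing on how quickly an effect would appear.

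**4. Is the order fixed anywhere?**
- Section 5.4: no order given.
- Section 6: randomisation before Part B participation, stated only for patients continuing from Part A, who number at most 12.
- Table 4: no randomisation row.
- Result: no text places baseline before randomisation or before the first home reading, and no text places it after.

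**The case against.** A reader might infer that baseline does follow randomisation, from the sentence in section 6 and from the intensive-arm call in the baseline column. The documents do not support this. The sentence in section 6 is about Part A patients only, at most 12 of 60, and does not say whether participation includes the baseline tests. The call proves little either: Table 3 puts the Part A call in the same column, yet section 5.7 says "At the end of week A1, participants will receive a phone call to ensure they are managing with the general process of sampling". The column therefore holds events from different days, and a call late in the week does not show that the arm was known when blood and questionnaire were taken.

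A reader might also infer that treatment biases the baseline between arms. It does not, because exposure and window are common to both.

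Several mitigating points stand:
- The start of home monitoring may in practice be tied to the baseline visit.
- Section 7 collects kidney function from records, at diagnosis and three months earlier, and the booklet in 14.6 promises participants an idea of their baseline when they start.
- Section 9 is framed in creatinine levels, and a comparison of end values is untouched.
- Time to AKI detection runs from the start of the treatment cycle, not from this visit.
- The investigator reviews alerts only weekly, which makes a large first-week effect on creatinine doubtful.
- The protocol proposes no baseline adjustment, so the hazard of adjusting for a post-randomisation value is only potential.

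These points soften the kidney-function side without removing it, since Table 2 starts the change at Week 1 and does not name the record values as the starting point. They do nothing for quality of life. An analysis plan cannot help either, because it cannot create a score that was not collected in time.

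**Conclusion.** The point holds as a gap in a stated rule: the plus side of the window applies to baseline, and nothing secures a measurement before allocation and before the first reading. Baseline can be taken with the arm known and after about 3, possibly 6, of 18 home readings, if monitoring starts at the beginning of Week 1.

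The consequence is clearest for quality of life, a secondary outcome, where the size and direction of any shift are unknown and no earlier score exists. For kidney function the likely effect is dilution of a change-from-baseline contrast, by an amount that the documents do not allow one to estimate. The illustrative losses rest on assumed linear build-up, assumed correlations and every participant at the limit. The variable interval and treatment exposure add noise in both arms, not bias between them. It is a cheap correction worth making, not a flaw that invalidates Part B.

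**What to change.** In section 5.2 and Table 4:
1. Require baseline blood, urine, blood pressure and the quality-of-life form to be completed before randomisation and before the first home reading.
2. Give the baseline visit no plus side; keep the window of one week either side for later visits.
3. Add a randomisation row to Table 4 after baseline, and show the intensive-arm phone call after that.
4. Record actual sampling dates, so that the true interval is known.

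The cost is wording and visit order, with no extra samples or patients. Sites lose some freedom to fit baseline to clinic appointments, which is what the window is for, and some participants would start home monitoring a few days later.

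Separately, reconcile the Part B visit weeks: section 5.2 gives B1, B3 and B6, and Table 4 gives Weeks 1, 4 and 8. The end of the change interval depends on which applies.
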